8.2.2 Study Drug Dose and Duration

All subjects enrolled in the Treatment Cohort will receive the same regimen of study drug that is being administered in the Phase 3 studies of VX-661 in combination with ivacaftor in subjects with CF who are 12 years of age or older. Subjects will receive a morning dose of VX-661 100 mg/ivacaftor 150 mg (FDC tablet) and an evening dose of ivacaftor 150 mg. These dosages were selected based on efficacy, safety, and tolerability results from Study VX11-661-101.¹⁸ The dose regimen of ivacaftor planned for this study (150 mg q12h) is the current labeled dose regimen for patients with CF with gating mutations who are 12 years of age and older. Dosages for subjects 12 to 17 years of age (same as the adult dosage) were determined based on the historical data on weight as a function of age in patients with CF from the ivacaftor Phase 3 program and the US CF Foundation Registry, weights in the 12- to 17-year old population are expected to be only slightly lower than those of the adult CF population.²⁰

All subjects in the Treatment Cohort will receive VX-661 in combination with ivacaftor. Subjects who received VX-661 in combination with ivacaftor in the parent study and continue to receive this combination in Study VX14-661-110 may receive treatment for up to approximately 2.5 years, providing further information on the safety and efficacy of long-term treatment with VX-661 in combination with ivacaftor.

8.2.3 Rationale for Study Assessments

The safety and PK assessments are standard parameters for clinical studies in drug development. The efficacy assessments are widely accepted and generally recognized as reliable, accurate, and relevant to the study of patients with CF.

[figure not shown]
Spirometry: As lung disease is the major cause of morbidity and mortality for patients with CF, CF lung disease is the desired primary target of VX-661/ivacaftor combination therapy. Spirometry (as measured by FEV₁) is the most widely implemented standardized assessment to evaluate lung function.

Nutritional Status (measured by weight and BMI): Malnutrition is common in patients with CF because of increased energy expenditures due to lung disease and fat malabsorption. Given that VX-661 in combination with ivacaftor is a systemic therapy, it has the potential to improve extrapulmonary manifestations of CF, including those in the gastrointestinal system. Improved

nutritional status, defined as an increase in weight and/or BMI, is considered an appropriate endpoint for therapies targeting CFTR and was used in previous clinical studies of CFTR-targeted therapies (Studies VX08-770-102 and VX08-770-103). To evaluate the effect of VX-661 in combination with ivacaftor on growth, change in weight and BMI will be measured.

As children gain weight and height as part of normal growth, adjustment for age and sex is necessary to assess changes in nutritional status in a population of boys and girls in varying stages of growth. To evaluate the effect of VX-661 in combination with ivacaftor on growth and nutrition adjusted for age and sex, weight-for-age, height-for-age, BMI-for-age, and the respective z-scores will be determined. Height and weight will be collected at the study visits indicated in the schedule of assessments.

CFQ-R: The CFQ-R is a frequently used CF-specific instrument that measures the health-related quality of life of patients with CF.^{21,22,23} As VX-661 in combination with ivacaftor is a systemic therapy, it has the potential to improve respiratory symptoms as well as other extrapulmonary manifestations of CF. These improvements can be captured by the non-respiratory symptoms domains of the CFQ-R. Linguistically validated versions of the CFQ-R^{24,25} are available, thereby allowing consistent interpretation of the results in this global study. The CFQ-R will be used to capture and evaluate the impact of VX-661 in combination with ivacaftor on patient report of respiratory symptoms and other aspects of health-related quality of life.

Other Events Related to Outcome: Pulmonary exacerbations, administration of antibiotic therapy for sinopulmonary signs and symptoms, and hospitalizations are other outcomes used to assess efficacy in therapies targeting improvement in CF disease. CF pulmonary exacerbations are a compilation of patient signs and symptoms that often result in the need for aggressive treatment, including the use of intravenous (IV) antibiotics administered at home, at the site, or in the hospital and/or pulmonary exacerbations that may require hospitalization. To date, there is no generally accepted objective definition of a pulmonary exacerbation,²⁶ and large multicenter CF clinical studies have used many variations of physician-derived definitions.^{27,28,29,30} Despite the lack of a standard definition, reduction in pulmonary exacerbation rate has served as a key clinical efficacy measure in definitive CF clinical studies, supporting the registration of 2 chronic CF pulmonary therapies (inhaled recombinant human DNase and inhaled tobramycin).²⁶ To evaluate the potential effect of VX-661 in combination with ivacaftor on pulmonary exacerbations, count, duration, and time-to-first event of hospitalizations and count and time-to-first event of IV courses of antibiotics for pulmonary exacerbations will be derived. For data consistency, this protocol specifies 1 definition of pulmonary exacerbation which is based on the definition used for the other studies including the ivacaftor monotherapy initial registration studies (Section 11.7.5.1). Because signs and symptoms in the definition may occur without meeting the overall definition of a pulmonary exacerbation, the number and timing of

outpatient sick visits to the clinic or hospital for CF that are unrelated to the study protocol will also be collected.

9 STUDY POPULATION

Eligibility will be reviewed and documented by an appropriately qualified member of the investigator's team before subjects are enrolled.

9.1 Inclusion Criteria

Subjects who meet all of the following inclusion criteria will be eligible for this study.

1. Signed and dated an informed consent form (ICF), and where appropriate, signed and dated an assent form.
2. Did not withdraw consent from the parent study.
3. Able to understand and comply with protocol requirements, restrictions, and instructions, and likely to complete the study as planned, as judged by the investigator and Vertex, based in part on study compliance in Studies VX13-661-103, VX14-661-106, VX14-661-107, VX14-661-108, VX14-661-109, VX14-661-111, or other Vertex studies investigating VX-661 in combination with ivacaftor.
4. The following criteria apply to the Treatment and Observational Cohorts:
 - Subjects entering the **Treatment Cohort** must meet all of the following criteria:
 1. Elect to enroll in the Treatment Cohort
 2. Completed study drug treatment during the Treatment Period in a parent study (Studies VX13-661-103, VX14-661-106, VX14-661-107, VX14-661-108, or VX14-661-109), study drug treatment and the Safety Follow-up Visit for subjects from Study VX14-661-111, or study drug treatment and follow-up as specified in other Vertex studies investigating VX-661 in combination with ivacaftor. (Note: studies VX11-661-101 and VX15-661-113 are not eligible parent studies.)
 - o Subjects who had study drug interruptions, but completed study visits up to the last scheduled visit of the Treatment Period of the parent study (and the Safety Follow-up Visit for subjects from Study VX14-661-111 or study drug treatment and follow-up as specified in other parent Vertex studies investigating VX-661 in combination with ivacaftor) are eligible.
 - o Subjects who had a study drug interruption at the last scheduled visit of the Treatment Period of the parent study, subjects who required interruption to be continued or initiated at Day 1 in Study VX14-661-110, or subjects who resumed study drug in the parent study after a study drug interruption due to elevated transaminases but who did not complete at least 4 weeks of rechallenge with study drug (due to the timing of the rechallenge versus the time remaining in the Treatment Period of the parent study) must meet eligibility criteria and have received approval from the Vertex medical monitor in order to be enrolled into the Treatment Cohort of Study VX14-661-110.

Note: Subjects who permanently discontinue study drug treatment during the parent study, including at the last visit of the Treatment Period are not eligible to enroll into the Treatment Cohort.

3. Willing to remain on a stable CF medication (and supplement) regimen through the Safety Follow-up Visit of Study VX14-661-110.
- Subjects **re-enrolling in the Treatment Cohort** must meet all of the following criteria:
 1. Previously received at least 4 weeks of study drug before discontinuing Study VX14-661-110 to participate in another qualified Vertex study, which is defined as a Vertex study of investigational CFTR modulators that allows participation of subjects in Study VX14-661-110. Note: other qualified Vertex studies do not include studies of lumacaftor in combination with ivacaftor or ivacaftor monotherapy.
 2. Completed the last required visit of another qualified Vertex study before or during the Returning Visit in Study VX14-661-110. (If the last required visit of the other qualified Vertex study is more than 60 days from the Returning Visit in Study VX14-661-110, approval of the medical monitor is required.) Subjects who discontinue Study VX14-661-110 to screen for another qualified Vertex study, and do not enroll into the other study, are eligible to re-enroll in Study VX14-661-110.
 3. Willing to remain on a stable CF medication (and supplement) regimen through the Safety Follow-up Visit of Study VX14-661-110.
 4. Subjects who discontinue Study VX14-661-110 more than once to participate in another qualified Vertex study may not re-enroll in Study VX14-661-110 a second time.
 - Subjects entering the **Observational Cohort** must meet the following criteria:
 1. <18 years of age (age on the date of informed consent/assent in the parent study)
 2. Completed study drug treatment during the Treatment Period in a parent study (Studies VX13-661-103, VX14-661-106, VX14-661-107, VX14-661-108, or VX14-661-109), study drug treatment and the Safety Follow-up Visit for subjects from Study VX14-661-111, or study drug treatment and follow-up as specified in other parent Vertex studies investigating VX-661 in combination with ivacaftor, but do not elect to enroll in the Study VX14-661-110 Treatment Cohort (note: Studies VX11-661-101, and VX15-661-113 are not eligible parent studies); or
 3. Received at least 4 weeks of study drug treatment and completed visits up to the last scheduled visit of the Treatment Period of a parent study (and the Safety Follow-up Visit for subjects from Study VX14-661-111 or study drug treatment and follow-up as specified in other parent Vertex studies investigating VX-661 in combination with ivacaftor), but do not meet eligibility criteria for enrollment into the Treatment Cohort

Note: Subjects who permanently discontinued study drug in the parent study must have completed the last scheduled study visit of the Treatment Period (and the Safety Follow-up Visit for subjects from Study VX14-661-111 or study drug treatment and

follow-up as specified in other parent Vertex studies investigating VX-661 in combination with ivacaftor).

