Treatment-emergent (TE) Period will include the time from the first active dose of VX-661/ivacaftor or ivacaftor alone (in the parent study or Study VX14-661-110, but after the washout period, if applicable) to the Safety Follow-up Visit or 28 days after the last dose of the study drug for subjects who do not have a Safety Follow-up Visit or who have their Safety Follow-up Visit more than 35 days after the last dose of Study VX14-661-110. For subjects who participate in another qualified Vertex study before completing Study VX14-661-110 (96 weeks) and re-enroll in Study VX14-661-110, the TE Period will exclude the time spent in the other study. Specifically, the TE Period will be interrupted 28 days after the last dose of study drug in Study VX14-661-110 and will restart with re-enrollment into Study VX14-661-110 when the subject takes the first dose of study drug.

Note, in the Efficacy Analysis and TE Periods, for subjects who received the active study drugs in Study VX14-661-108, the first active dose will be the first dose of VX-661/ivacaftor or ivacaftor monotherapy in the Treatment Period 2 of Study VX14-661-108. For subjects who received the active study drug from Study VX13-661-103, the first active dose will be the first active dose of study drug in the Open-label Phase of Study VX13-661-103.

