8 ANALYSIS PERIODS

8.1 Efficacy Analysis Period

110 Efficacy Analysis Period is defined as the time period from the 1st dose of study drug in Part A to the date of last efficacy assessment in Part A.

For subjects who participate in another qualified Vertex study before completing Study 110 assessments and re-enroll in Study 110, 110 Efficacy Analysis Period will exclude the time between the last dose before the discontinuation from Study 110 and the first dose after re-enrollment in Study 110.

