8.2 Pulmonary Exacerbation Analysis Period

PEx Efficacy Analysis Period is defined as the time period from the first dose of TEZ/IVA in parent study (after the washout period, if applicable) or Study 110 Part A to the date of last efficacy assessment in parent study or Study 110 Part A, as highlighted in grey in [Table 8-1](#). Note for parent Study 108, only Period 2 is pooled.

Similarly, for subjects who participate in another qualified Vertex study before completing Study 110 assessments and re-enroll in Study 110, the PEx Efficacy Analysis Period will exclude the time between the last dose before the discontinuation from Study 110 and the first dose after re-enrollment in Study 110.

Table 8-1 PEx Analysis Period for PEx Analysis Sets			
Analysis Set	Analysis Period		
	Parent Study		Study 110 Part A
106/110 PEx Analysis Set	TEZ/IVA		TEZ/IVA
	PBO		TEZ/IVA
108/110 PEx Analysis Set	Period 1: TEZ/IVA	Period 2: IVA	TEZ/IVA
	Period 1: IVA	Period 2: TEZ/IVA	TEZ/IVA
	Period 1: TEZ/IVA	Period 2: PBO	TEZ/IVA
	Period 1: PBO	Period 2: TEZ/IVA	TEZ/IVA

	Period 1: IVA	Period 2: PBO	TEZ/IVA
	Period 1: PBO	Period 2: IVA	TEZ/IVA

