- Derivations of measurements at scheduled visits per specified visit windowing rules;
- Derivations of baseline/last on-treatment measurements;
- Derivations of the maximum/minimum on-treatment values and maximum/minimum changes from baseline values for safety analyses;
- Data listings where appropriate.

Treatment-emergent (TE) Period will include the time from the first active dose of VX-661/ivacaftor or ivacaftor alone (in the parent study or Study VX14-661-110, but after the washout period, if applicable) to the Safety Follow-up Visit in Part A or 28 days after the last dose of the study drug for subjects who do not have a Safety Follow-up Visit or who have their Safety Follow-up Visit more than 35 days after the last dose in Part A of Study VX14-661-110. For subjects who participate in another qualified Vertex study before completing Part A of Study VX14-661-110 (96 weeks) and re-enroll in Study VX14-661-110, the TE Period will exclude the time spent in the other study.

110 Treatment-Emergent (TE) Period is defined as the time from 1st dose of study drug in Part A to SFU in Part A or 28 days after the last dose of the study drug for subjects who do not have a SFU Visit or who have their SFU Visit more than 35 days after the last dose in Part A. For subjects who participate in another qualified Vertex study before completing Part A (96 weeks) and re-enroll in Study 110, the TE Period will exclude the time spent in the other study. The **efficacy analysis baseline** is defined as the most recent non-missing measurement (scheduled or unscheduled) collected prior to the first dose of study drug in the parent studies for all subjects, except for subjects randomized to the placebo arm in Study 106.

The efficacy analysis baseline for subjects randomized to the Study 106 placebo arm is defined as the most recent non-missing measurement (scheduled or unscheduled) collected prior to the first dose of study drug in Study 110.

The **safety analysis baseline**, unless otherwise specified, is defined as the last non-missing assessment prior to the first dose of active treatment (TEZ/IVA or IVA) from the parent study (after the wash-out period, where applicable) or Study 110, whichever is earlier.

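### Gap-exclusion rules cover only re-enrollers who participated in another study, so the off-drug gap of a subject who left only to screen stays in the exacerbation and treatment-emergent periods

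*Protocol*

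**What the plan says.** **Who may return.** Protocol 9.1 lists criteria for re-enrolling in the Treatment Cohort. Criterion 1 reads "Previously received at least 4 weeks of study drug before discontinuing Study VX14-661-110 to participate in another qualified Vertex study". Criterion 2 asks for the last required visit of the other study to be complete, then adds the screen-only route: "Subjects who discontinue Study VX14-661-110 to screen for another qualified Vertex study, and do not enroll into the other study, are eligible to re-enroll".

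**Which gaps are removed.**
- SAP 8.2 (exacerbation period): the exclusion from last dose before leaving to first dose after return is "for subjects who participate in another qualified Vertex study before completing Study 110 assessments and re-enroll in Study 110".
- SAP 8.1 (110 Efficacy Analysis Period): the same condition, "For subjects who participate in another qualified Vertex study before completing Study 110 assessments and re-enroll in Study 110".
- SAP 9.1 (110 TE Period): the provision opens "For subjects who participate in another qualified Vertex study before completing Part A (96 weeks) and re-enroll in Study 110, the TE Period will exclude"; what it takes out is only the subject's stay in that study.
- Protocol 12.3.1 (TE Period): "For subjects who participate in another qualified Vertex study before completing Study VX14-661-110 (96 weeks) and re-enroll". It then specifies that the period is interrupted 28 days after the last dose and restarts at the first dose after re-enrolment. The protocol's Efficacy Analysis Period carries the same participation condition.

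**Where the periods are used.** SAP 9.6.2.2 takes the logarithm of the exacerbation period's duration as the offset. SAP 9.6.1.5 and 9.6.2.3 count days to first exacerbation on TEZ/IVA within that period. SAP 9.7.1 classes an adverse event as treatment-emergent if it arises from the first Part A dose through the end of the 110 TE Period.

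**The concern.** The eligibility rule recognises a returner who never entered another study, and no analysis-period rule names that subject. Two subjects with the same off-drug interval would then be handled differently only because one passed screening elsewhere and the other did not. At stake are the exacerbation rate, the time to first exacerbation described as on TEZ/IVA, and the sorting of adverse events into treatment-emergent or not. Safety is the primary objective, so the TE boundary should not be left for a programmer to infer.

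**Working it through.** The plan gives no figure to reproduce here: there is no power calculation and no count of re-enrollers. The check compares the definitions and then gives an illustrative person-time calculation.

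**1. Scope of each rule.**

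| Rule | Applies to | Removes | Effect for a screen-only returner, read literally |
|---|---|---|---|
| Protocol 12.3.1, Efficacy Period | Those who participate elsewhere and re-enrol | Last dose to first dose after return | Nothing removed |
| Protocol 12.3.1, TE Period | Same | Time beyond 28 days after last dose, until re-dosing | Nothing removed |
| SAP 8.1, Efficacy Period | Same | Last dose to first dose after return | Nothing removed |
| SAP 8.2, exacerbation period | Same | Last dose to first dose after return | Nothing removed |
| SAP 9.1, TE Periods | Same | Time spent in the other study | Nothing removed |

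The re-enroller provisions for prior medication (Protocol 12.3.3.3) and pretreatment adverse events (Protocol 12.3.5.1) carry the same condition.

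**2. Consequence for event classification.** Re-enrollers must re-consent (Protocol 11.2), and adverse-event collection starts at consent (13.1.1.3). An event between re-consent and re-dosing therefore falls inside an unbroken 110 TE Period and is a TEAE under SAP 9.7.1. For a subject who participated elsewhere, Protocol 12.3.5.1 calls the same event pretreatment.

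**3. What is collected in the gap.** The Safety Follow-up waiver requires enrolment in the other study (Table 3-1 footnote e; Protocol 8.1.1.2), so it does not reach this group. They still owe that visit at 28 (±7) days, or an Early Treatment Termination (ETT) Visit at 3 weeks or later that replaces it. Adverse events are collected to that point. Exacerbation-related events are scheduled at the ETT, Safety Follow-up and Returning Visits, with no look-back period stated.

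**4. Size for one subject.** Let g be the gap in weeks and 96 the planned weeks on drug. If no event is recorded in the gap, the rate is understated by g/(96 + g):
- g = 4: 4/100 = 4.0%
- g = 12: 12/108 = 11.1%
- g = 24: 24/120 = 20.0%

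**5. Size for a group.** With share f affected, the pooled rate (total events over total time) is understated by fg/(96 + fg):
- f = 1%, g = 12: 0.12/96.12 = 0.12%
- f = 5%, g = 12: 0.60/96.60 = 0.62%
- f = 5%, g = 24: 1.20/97.20 = 1.23%
- a more extreme case, f = 10%, g = 26: 2.60/98.60 = 2.64%

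Both f and g are assumptions. Protocol 9.1's 60-day approval condition runs from the other study's last required visit, so it does not clearly bound this gap. For subjects already on TEZ/IVA in the parent study, the exacerbation period also includes that earlier time, which makes these percentages smaller.

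**6. Size for TE time.** The protocol keeps the first 28 days off drug as TE time for other returners too. The literal difference is therefore g − 4 weeks: 0, 8 and 20 weeks for gaps of 4, 12 and 24 weeks.

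**The case against.** **The intent may already cover this group.** Re-enrollers must meet all criteria, and criterion 1 describes them as having left to participate in another study. The study-day clock also pauses for every re-enroller. This is a fair reading of intent, and it means the defect arises from silence and not from an express instruction to count the gap. It does not settle the matter. Criterion 1 states a purpose for leaving, whereas the period rules apply to those who do participate. Even if a screener counted as a participant, the SAP says only that "the TE Period will exclude the time spent in the other study". For someone never enrolled there, that is nil, or at most the screening time. The SAP omits the protocol's 28-day interruption and restart sentence.

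**A stronger reading does not hold.** A reader might infer that the whole gap is unobserved and is analysed as event-free time on TEZ/IVA, lowering exacerbation and TEAE rates throughout. The documents do not support that:
- Follow-up continues to about 28 (±7) days after the last dose, exacerbations are queried again on return, and related SAEs stay reportable after the Safety Follow-up Visit (Protocol 13.1.2.2). A gap exacerbation reported on return would be counted against TEZ/IVA, so the bias could go either way.
- The continuous efficacy endpoints are analysed by visit and have no person-time denominator. They are essentially unaffected.
- The exposure duration in SAP 9.5 runs from first to last dose regardless of interruption, for every re-enroller. Any dilution through that quantity is a separate matter, and the denominator of the exposure-adjusted rates is not spelled out.

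**The group may be tiny or empty.** Subjects may screen while remaining in the Treatment Cohort (Protocol 8.1.1.1), so leaving in order to screen is not required. The study makes no between-group hypothesis tests. Both points stand and keep the severity low.

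**Conclusion.** The point holds as a minor scope error in the period definitions. It affects the exacerbation rate, time to first exacerbation on TEZ/IVA, and TE classification beyond 28 days after the last dose.

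The number of screen-only returners and their gap lengths are not given. With 96 weeks on drug, no events recorded in the gap, and 1% to 5% of subjects affected with gaps of 12 to 24 weeks, a group rate moves by about 0.1% to 1.2%. If gap events are reported, the shift could be smaller or reversed. No conclusion of the study is likely to turn on it. The reason to act is that like intervals should be treated alike and the correction is nearly free.

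**What to change.** 1. In SAP 8.2 and 9.1, and for consistency SAP 8.1 and Protocol 12.3.1, apply the exclusion to any discontinuation of Study 110 followed by re-enrolment, whether or not the subject entered another study. Align the re-enroller wording in Protocol 12.3.3.3 and 12.3.5.1.
2. In the SAP definition of the 110 TE Period, replace the reference to time in the other study with the rule in Protocol 12.3.1 for all re-enrollers: interrupt 28 days after the last dose and restart at the first dose after return.
3. State whether the exposure duration in SAP 9.5 and the denominator of the exposure-adjusted event rates follow the same rule.

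The cost is a sentence in each definition. The programming is already needed for the other returners. It would also help to report how many screen-only returners there were and how long their gaps lasted.
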